2.3 Exploratory

- Characterize the pharmacokinetics of GT0918 and its metabolite GT0955
- Characterize emergence of viral resistance to GT0918
- Explore biomarkers predictive of GT0918 safety, efficacy, and/or disease progression and COVID-19 clinical outcomes

3 INVESTIGATIONAL PLAN

3.1 Overall Study Design and Plan

This is a randomized, placebo-controlled two-arm study with the objective to evaluate the efficacy and safety of GT0918 in outpatients with mild or moderate COVID-19 illness.

The population of subjects with mild to moderate COVID-19 illness will be chosen to evaluate if anti-androgen therapy may effectively prevent progression to the severe form of COVID-19 illness by treating this population early in their disease course and prior to respiratory compromise and failure.

The study is a multicenter trial that will be conducted in the United States (US) and other countries. Approximately 668 subjects will be randomized in a 1:1 ratio to either GT0918 or placebo. There will be an interim analysis after 334 subjects completing Day 28 after the first dose to allow early stopping for futility, efficacy, or safety. The blood samples for PK analysis need to be collected for at least 200 subjects, whom will also be randomized into the interventional treatment or placebo group with 1:1 ratio.

Subjects will be randomized into 1 of 2 arms with 1:1 ratio, each will receive an interventional treatment/placebo.

Randomization will be stratified by the following factors:

- Sex: Male or Female
- Race and ethnicity (non-Hispanic White or others /Hispanic or Latino /non-Hispanic Black)
- Number of risk factors 0, 1-2, ≥ 3 (based on CDC defined conditions <https://www.cdc.gov/coronavirus/2019-ncov/need-extra-precautions/people-with-medical-conditions.html>). Adults of any age with the following conditions are at increased risk of severe illness from the virus that causes COVID-19:
 - Age ≥ 65 years
 - Cancer
 - Chronic kidney disease
 - Chronic lung diseases, including COPD (chronic obstructive pulmonary disease), asthma (moderate to severe), interstitial lung disease, cystic fibrosis, and pulmonary hypertension
 - Dementia or other neurological conditions
 - Down Syndrome
 - Heart conditions, such as heart failure, coronary artery disease, or cardiomyopathies or hypertension
 - Immunocompromised state (weakened immune system) from solid organ transplant
 - Liver disease
 - Overweight and Obesity (body mass index [BMI] ≥ 25 kg/m²)
 - Sickle cell disease or thalassemia
 - Smoking, current or former
 - Diabetes Type 1 or 2
 - HIV infection
 - Solid organ or blood stem cell transplant
 - Stroke or cerebrovascular disease, which affects blood flow to the brain
 - Substance use disorders
 - Others per most updated list from CDC website as above

GT0918 will be supplied as 100 mg tablets as individual patient supply packaged in blister. GT0918/placebo will be given orally once daily on Days 1-14 during the study period. Days 15-28 will be the post-treatment period without dosing with GT0918/placebo. The safety follow-up will be up to 28 days after last dose making the overall duration of monitoring 42 days for each patient.

The study treatment period is shown as below.

[figure not shown]

Figure 1: Overview of Study Period and Group Assignment

3.2 Planned Interim Analysis

An interim analysis will be conducted when 334 subjects complete Day 28 after first dose. The objective of the interim analysis to assess safety, futility, efficacy, sample size adjustment as well as potential enrichment of the population to enroll a population at higher risk for an infection requiring hospitalization or oxygen support in case the observed rates for the primary endpoint in the control arm are lower than expected. An independent data monitoring committee (IDMC) will review the unblinded interim analysis report to assess the objectives of the interim analysis and provide recommendations about early study closure, change study population, or change study sample size.

The futility criterion for the study will be based on the conditional power of the study being <10%.

The efficacy criterion will be based on the one-sided p-value of the primary endpoint analysis as <0.0015. The boundary is estimated based on O'Brien and Fleming type alpha spending method. In this case the stopping boundary for efficacy is met and the study could be stopped for efficacy. Assuming there is no change in the study design regarding sample size modification, the one-sided p-value of <0.024 will be used for the final analysis to conclude the efficacy of the treatment group.

The conditional power will be evaluated based on primary endpoint in the interim analysis. If the conditional power of the study at the time interim analysis is between 50% to 80% (promising zone approach), the sample size could be increased to a maximum of 1500 subjects based on the efficacy in the interim analysis for overall population. If the conditional power of the study is above 80% power and the stopping boundary for efficacy is not met, the sample size will not be changed.

Rigorous steps will be taken (e.g., firewalls) where possible to minimize the information that can be inferred by observers.

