## 10. STATISTICAL METHODS AND DATA ANALYSIS

### 10.1 General Considerations

It is planned that the data from all centers participating in the study will be combined, so that an adequate number of patients are available for analysis. Kintor and/or a designated CRO will perform all analyses. And data analyses performed independently by any investigator should be submitted to Kintor before publication or presentation.

A Statistical Analysis Plan (SAP) will be prepared after the protocol is approved. It will provide further details regarding the definition of analysis variables and analysis methodology to address all study objectives. The SAP will serve as a compliment to the protocol and supersedes it in case of differences.

The statistical evaluation will be performed using the Statistical Analysis Software (SAS®) Version 9.4 or higher (SAS Institute, Cary, NC). All data will be listed, and summary tables will be provided. Summary statistics will be presented by dose group. For continuous variables, data will be summarized with the number of subjects (N), mean, standard deviation, median, minimum, and maximum by treatment group. For categorical variables, data will be tabulated with the number and percentages of subjects for each category by treatment group.

Interim Analysis will be conducted based on the Data Monitoring Committee SAP.

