Assuming there is no change in the study design regarding sample size modification, the p-value of 0.0245 will be used to conclude the efficacy of the treatment arm. O'Brien-Fleming Alpha Spending Function was used to calculate the efficacy boundary and the resulting alpha levels for the interim analysis and the final analysis.

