4.10 Efficacy Evaluation

4.10.1 Analysis and Data Conventions

Primary Null Hypothesis H0: proportion of subjects who do not experience all-cause hospitalization (defined as ≥ 24 hours), do not require supplemental oxygen for ≥ 24 h in response to $\text{SpO}_2 \leq 93\%$ and are alive by Day 28 in the GT0918 arm (p1) is equal to the proportion in the placebo arm (p2)

Primary Alternative Hypothesis Ha: the proportion of subjects who do not experience all-cause hospitalization (defined as ≥ 24 hours), do not require supplemental oxygen for ≥ 24 h in response to $\text{SpO}_2 \leq 93\%$ and are alive by Day 28 in GT0918 arm (p1) is greater than the proportion in the placebo arm 2 (p2)

Mathematically written as:

$$H_0: p_1 - p_2 = 0$$

$$H_a: p_1 - p_2 > 0$$

The primary endpoint event rate will be compared between treatment and placebo arm using Cochran–Mantel–Haenszel (CMH) Chi-square test using age and the stratification factors at time of randomization at the one-sided 0.025 level based on mITT set. P-values and 95% exact confidence intervals for the treatment difference will be presented. The actual alpha level used for the final analysis will take into account the adjustment required for the interim analysis.

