4.10.1.2 Multiple Comparisons/Multiplicity

One interim analysis is planned. The method of adjusting the Type I error rate used in this study is O'Brien and Fleming type alpha spending. The actual alpha spending will be calculated based on the actual information used for the interim analysis.

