- Subjects with missing primary assessments by day 28 will be treated as meeting primary endpoint. The primary endpoint event rate will be compared between treatment and placebo arm using CMH Chi-square test with adjusting age and the stratification factors (sex, race and ethnicity, and number of risk factors) at time of randomization. The hypothesis test will be performed at the one-sided 0.025 level based on mITT. Odd ratio with 95% exact confidence interval and p-value will be presented.
- The number and proportion of subjects that do not experience any of the 3 components (all-cause hospitalization, requirement of supplemental oxygen and death) of the primary endpoint by Day 28 will be summarized by treatment for the mITT population in frequency tables and listed.
- The individual components of the primary endpoint will be summarized as well.

The following sensitivity analysis will be performed for the primary endpoint:

- Among subjects with dosing days > 7 days;
- Per protocol analysis set;
- Complete case analysis set (subjects without any missing primary endpoint assessments);
- Removing the constraint of ≥ 24 hours in hospitalization and supplemental oxygen use;
- By treating missing primary assessments as hospitalization;
- By treating missing primary assessments as hospitalization and among subjects with dosing days > 7 days.

All sensitivity analyses will be performed using mITT sets except the per protocol analysis. Also, all sensitivity analyses will be conducted using the same one-sided CMH chi-square tests introduced for the primary endpoint analysis.

Interim analysis

An interim analysis will be conducted when 334 subjects complete Day 28 after first dose to assess safety, futility, efficacy, sample size adjustment as well as potential enrichment of the population to enroll a population at higher risk for an infection requiring hospitalization or oxygen support in case the observed rates for the primary endpoint in the control arm are lower than expected. An IDMC will review the unblinded interim analysis report to assess the objectives of the interim analysis and provide recommendations about early study closure, change study population, or change to study sample size.

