The one-sided Type I error rate (0.025) for the primary efficacy endpoint will be adjusted following O'Brien and Fleming type alpha spending method. The actual alpha spending will be calculated based on the actual information used for the interim analysis and used as the efficacy boundary, as shown below. The efficacy criterion will be based on the one-sided p-value of the primary endpoint analysis as less than the actual alpha spending. In this case the stopping boundary for efficacy is met and the study could be stopped for efficacy.

$$\text{O'Brien and Fleming: } \alpha_{IA}(t^*) = 2 - 2\Phi(Z_{1-\alpha/2}/\sqrt{t^*}),$$

where IA means interim analysis, Φ denotes the standard normal cumulative distribution function and t^* denotes the fraction of information that has been observed at Interim Analysis timewpoint.

The futility of a study that is underway can be determined by calculating its conditional power, which is the probability of statistical significance at the completion of the study given the data obtained so far. The futility criterion for the study will be based on the conditional power of the study being <10%. The conditional power will be evaluated based on primary endpoint in the interim analysis. If the conditional power of the study at the time interim analysis performed is between 50% to 80% (promising zone approach), the sample size could be increased to a maximum of 1500 subjects based on the efficacy in the interim analysis for overall population. If the conditional power of the study is above 80% power and the stopping boundary for efficacy is not met, the sample size will not be changed. The general lower one-sided conditional power is computed as

$$CP_{IA}(\theta) = \Phi\left(\frac{-Z_{IA}\sqrt{I_{IA}} - z_{1-\alpha}\sqrt{I_{FA}} - \theta(I_{FA} - I_{IA})}{\sqrt{I_{FA} - I_{IA}}}\right),$$

where

IA representing interim analysis and FA representing final analysis,

$\theta = P_2 - P_1$ (the expected difference under the alternative hypothesis),

$Z_{IA} = (p_{2IA} - p_{1IA})\sqrt{\hat{I}_{IA}}$ (the z-statistic computed from the observed data),

$I_{IA} = \frac{1}{\sigma^2} \left(\frac{1}{n_{1IA}} + \frac{1}{n_{2IA}} \right)^{-1}$ (the interim information level),

$I_{FA} = \frac{1}{\sigma^2} \left(\frac{1}{n_1} + \frac{1}{n_2} \right)^{-1}$ (the final information level),

where

p_{jIA} is the sample proportion for group j, estimating p_j at IA,

\hat{I}_{IA} is the estimated information from the sample at IA,

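### SAP 3.2 prints the final one-sided threshold as <0.024, while the SAP's own spending function at 334/668 and protocol 10.8 give 0.0245; the fixed figures should be tied to the actual information fraction

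*SAP*

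**What the plan says.** SAP 3.2 plans one interim analysis when 334 subjects have completed Day 28, with a one-sided efficacy level of 0.0015. If the sample size is not modified, "the one-sided p-value of <0.024 will be used for the final analysis to conclude the efficacy of the treatment group". Protocol 10.8, for the same case and the same type of spending function, says that "the p-value of 0.0245 will be used to conclude the efficacy of the treatment arm". On precedence, protocol 10.1 states: "The SAP will serve as a compliment to the protocol and supersedes it in case of differences".

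Three other places in the SAP make the levels depend on what happens at the interim:

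- SAP 4.10.1: "The actual alpha level used for the final analysis will take into account the adjustment required for the interim analysis".
- SAP 4.10.1.2: "The actual alpha spending will be calculated based on the actual information used for the interim analysis".
- SAP 4.10.2 gives the spending function explicitly and says the interim spend is to be calculated "based on the actual information used for the interim analysis and used as the efficacy boundary".

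SAP 3.2 and 4.10.2 also allow an increase to at most 1500 subjects when conditional power is between 50% and 80%. The only final level printed is the one for no change. Protocol 10.8 places the re-estimation rule in the DMC charter, and the consequences for the analysis in a separate document to be attached to the SAP.

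**The concern.** The final threshold is the success criterion for the primary claim, and the two documents print different values for the same situation. Since the SAP prevails, 0.024 is formally the rule. A one-sided final p-value of, say, 0.0242 would then fail under SAP 3.2 and succeed under protocol 10.8 and under the SAP's own function. That choice should not be open when the result is known.

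SAP 3.2 also prints both levels as fixed numbers without saying that they belong to a look at exactly half the information. If the interim fell elsewhere, neither 0.024 nor 0.0245 is the exact final level. The documents do not give the actual interim count.

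**Working it through.** **Inputs.** Overall one-sided alpha 0.025 and the spending function (SAP 4.10.2); one interim (SAP 4.10.1.2); 334 of 668 subjects, so t = 0.50 (SAP 3.2 and 4.12); event-free rates of 97% and 91%, 1:1 allocation (SAP 4.12 and 3.1).

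**1. Interim level.** The function is alpha(t) = 2 − 2Φ(z/√t), with z the 1 − 0.025/2 normal quantile, 2.2414. At t = 0.5, 2.2414/0.7071 = 3.170, so alpha(0.5) = 0.001525 (boundary z = 2.963). This reproduces the printed 0.0015.

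**2. Final level.** Solve P(Z1 > 2.963 or Z2 > c) = 0.025 under the null, with correlation √0.5 between Z1 and Z2. The solution is c = 1.9686, a nominal level of 0.0244998. With the interim boundary at exactly 0.0015 it is 0.02451. The protocol's 0.0245 reproduces; 0.024 does not to four decimals.

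**3. Other possible sources of 0.024.**

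- The classical O'Brien-Fleming design gives a final 0.0240, but an interim level of 0.0026.
- The SAP function gives 0.0240 at t = 0.576 (about 385 subjects), where the interim spend is 0.0031.
- Simple subtraction gives 0.025 − 0.0015 = 0.0235.

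None of these yields 0.0015 and 0.0240 together. Rounding 0.0244998 to three decimals does yield 0.024.

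**4. Effect at t = 0.50.** Overall alpha is 0.0245 with a final level of 0.024 and 0.0250 with 0.0245. For power, the drift is 0.06/√[(0.97×0.03 + 0.91×0.09)/334] = 0.06/√(0.111/334) = 3.291. Two-stage power is 90.61% at 0.024 and 90.75% at 0.0245, a difference of about 0.15 points (0.145 before rounding).

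**5. Other information fractions, same function.**

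| t | Subjects | Interim level | Final level |
|---|---|---|---|
| 0.45 | 301 | 0.00083 | 0.02472 |
| 0.50 | 334 | 0.00153 | 0.02450 |
| 0.55 | 367 | 0.00251 | 0.02419 |
| 0.60 | 401 | 0.00381 | 0.02380 |

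Take t = 0.60 with the interim level recomputed to 0.0038, as SAP 4.10.2 requires, but the final level left fixed. Overall alpha, P(Z1 > c1 or Z2 > c2) with correlation √0.60, is then 0.0252 at 0.024 and 0.0257 at 0.0245. If the interim level were also left at 0.0015, the same formula gives 0.0243 with a final 0.024. The small excess therefore comes from recomputing one level and not the other.

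**6. If the sample size is increased (conditional).** The conditional power formula is that of SAP 4.10.2, with variance 0.94 × 0.06 = 0.0564, 167 and 334 subjects per arm, and critical value 1.960. Let R = N/668. Without an interim rejection, the final statistic is (Z1√0.5 + B)/√R, with B normal, mean 0 and variance R − 0.5 under the null. Futility is treated as non-binding. With the ordinary test at 0.0245 and N raised throughout the 50–80% zone, type I error is:

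| Effect used in conditional power | Zone for Z1 (favouring GT0918) | N = 800 | N = 1000 | N = 1500 |
|---|---|---|---|---|
| Design difference | 0.46 to 1.30 | 0.0259 | 0.0266 | 0.0271 |
| Observed trend | 1.39 to 1.81 | 0.0246 | 0.0242 | 0.0235 |

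With design-effect conditional power and an increase only where it is 65–80%, the figures are 0.0254, 0.0255 and 0.0255.

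**The case against.** The strongest defence is that 0.024 is a correct three-decimal rounding, that it errs on the safe side, and that the precedence clause removes any ambiguity. A p-value in the disputed window has probability of only about 0.0005 under the null (0.0250 − 0.0245) and 0.0014 at the design rates (0.9075 − 0.9061). Moreover, if the recomputation rule is what operates, 0.024 is only a planning figure. Most of this stands and is why the point is minor. It does not dispose of the point. A rounded figure used as a decision threshold changes the decision rule, SAP 4.2 itself reports p-values to four decimals, and SAP 3.2 does not say that its figures are planning values.

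Three stronger readings are tempting and are not supported:

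- **That the printed threshold inflates type I error.** At the planned look it does the opposite.
- **That the primary test is run at an unadjusted 0.025.** SAP 4.10.2 does say: "The hypothesis test will be performed at the one-sided 0.025 level based on mITT". But the interim text of the same section says that this error rate is adjusted by the spending method, and SAP 4.10.1 says the same of the final level. No edit is needed there.
- **That the plan leaves a re-sized trial unprotected.** The stratified CMH test is specified without regard to sample size, so only the level or adjustment is missing. Protocol 10.8 assigns that matter to the DMC charter and an SAP attachment. Neither is among the documents reviewed, and either may contain a protected method.

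**Conclusion.** The mismatch is real and minor. SAP 3.2's <0.024 does not agree to four decimals with the SAP's own function or with protocol 10.8, both of which give 0.0245. With the interim at half the information and the sample size unchanged, the cost is about 0.0005 of alpha left unspent and about 0.15 points of power. Type I error stays protected. The power figure assumes the design rates and the unpooled normal approximation.

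The fixed presentation is a second small defect. It matters only if the interim was not at 334 of 668 and only one of the two levels was recomputed; at t = 0.60 a fixed final 0.024 would then give 0.0252.

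On an increased sample size, a reader might infer that type I error is inflated. That is possible but not shown. The ordinary test reaches about 0.027 only if conditional power is taken at the design difference, as SAP 4.10.2 defines it, and N is raised substantially throughout the zone. The excess is smaller if N is raised only in part of the zone, and there is none with observed-trend conditional power. This part lapses if N was not increased, and nothing in the documents shows that it was.

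**What to change.** In SAP 3.2, print the final level as 0.0245. Mark 0.0015 and 0.0245 as the values for t = 0.50 (334 of 668), both to be recomputed from the spending function in SAP 4.10.2 at the actual information fraction. This is a wording change with no cost to the trial, and it restores the full 0.025.

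Optionally, in SAP 3.2 or 4.10.2, cite the DMC charter or the SAP attachment named in protocol 10.8 as the source of the final level or adjustment if N is increased. If neither protects 2.5%, prespecify a valid method before unblinding. One example is to combine the stage-wise CMH z-statistics with pre-planned weights, √0.5 each for a look at 334 of 668; other valid methods would also do. This has no cost if N was not changed.

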3.3 Endpoints

3.3.1 Primary

- Percentage of subjects who do not experience any of the following events due to all causes by Day 28:
 - Hospitalization for \geq 24 hours or
 - Supplemental oxygen for \geq 24 hours in response to $\text{SpO}_2 \leq 93\%$ or
 - Death

3.3.2 Secondary

Hospitalization Percentage

- Percentage of subjects who experience any of the following events due to all causes by Day 28:
 - Hospitalization for \geq 24 hours or
 - Supplemental oxygen for \geq 24 hours in response to SpO₂ \leq 93% or
 - Death

Virologic Response

- Change from baseline to Days 3, 7, 14 and 28 in SARS CoV-2 viral load
- Proportions of subjects that achieve sustained 100% SARS-CoV-2 viral reduction at Days 3, 7, 14 and 28
- Time to sustained 100% SARS-CoV-2 viral reduction
- Proportion of subjects that achieve SARS-CoV-2 clearance (Days 3, 7, 14 and 28)
- Time to SARS-CoV-2 clearance
- SARS-CoV-2 viral load area under the concentration-time curve (AUC) assessed to days 3, 7, 14 and 28

NIAID Ordinal Scale

- Percentage of subjects achieving each clinical status at Days 3, 7, 14 and 28 as defined below based on The National Institute of Allergy and Infectious Diseases (NIAID) 8- point ordinal scale
 - 1 Death
 - 2 Hospitalized, on invasive mechanical ventilation or extracorporeal membrane oxygenation (ECMO)
 - 3 Hospitalized, on non-invasive ventilation or high flow oxygen devices
 - 4 Hospitalized, requiring supplemental oxygen
 - 5 Hospitalized, not requiring supplemental oxygen - requiring ongoing medical care (COVID-19-related or other medical conditions preventing hospital discharge)
 - 6 Hospitalized, not requiring supplemental oxygen - no longer requires ongoing medical care
 - 7 Not hospitalized, limitation on activities and/or requiring home oxygen
 - 8 Not hospitalized, no limitations on activities
- Proportion of subjects with all-cause hospitalization (defined as \geq 24 hours) by Day 28
- Proportion of subjects with COVID-19 related hospitalization (defined as \geq 24 hours) by Day 28
- Days of hospitalization due to all causes or COVID-19 by Day 28
- Time to hospitalization due to all causes or COVID-19 by Day 28
- Proportion of subjects requiring supplemental oxygen, high-flow oxygen, any ventilation or ECMO due to COVID-19 by Day 28

Symptom Questionnaire

- Symptom Improvement:
 - Change in symptom score (total of ratings) from baseline to Days 3, 7, 14 and 28
 - Time to symptom improvement

- Proportion of subjects demonstrating symptom improvement via the symptom questionnaire (total of ratings) on Days 3, 7, 14 and 28
- Symptom Resolution:
 - Proportion of subjects demonstrating symptom resolution via the symptom questionnaire on Days 3, 7, 14 and 28
 - Time to symptom resolution

Safety

- Safety assessments such as AEs, SAEs and laboratory data

